### 4.2.3. SERUM CHEMISTRY AND HEMATOLOGY

Evaluation of serum chemistry and hematology will be conducted at Screening, Day 0, Day 30, Day 90 and 9 months. Evaluations will be conducted at a local laboratory at each site.

Serum chemistry evaluations will include: calcium, glucose, sodium, potassium, chloride, bicarbonate, blood urea nitrogen (BUN), creatinine, alanine aminotransferase (ALT), aspartate aminotransferase (AST), total bilirubin, alkaline phosphatase, albumin, and total protein.

Hematology evaluations will include: complete blood count (CBC): red blood cells (RBC); hemoglobin (Hgb), hematocrit (HCT), mean corpuscular volume (MCV), mean corpuscular hemoglobin (MCH), mean corpuscular hemoglobin concentration (MCHC), platelets and white blood cells (WBC) with differential. Abnormal readings do not necessarily constitute an adverse event; the results need to be reviewed in the context of the subject's health.

Laboratory testing by visit is provided in [Appendix 1](#).

### 4.2.4. SERUM HGF

Serum HGF will be determined by ELISA at the following follow-up visits: immediately pre-treatment on Day 0, immediately pre-treatment on Day 7, immediately pre-treatment on Day 14, immediately pre-treatment on Day 21, on Day 30, Day 60, and Day 90. A minimum 6 cc blood draw will be taken at each time point. Allow blood to clot for 30 – 60 minutes at room temperature then centrifuge for 10 minutes at 1000 x g. Divide the isolated serum into six (6) equal aliquots of ~0.3 mL each. (0.5mL plastic storage tubes provided). Samples should be labeled with subject ID, draw date, study number and visit interval (*i.e.*, Day 0, 7, 14, 21, 30, 60 or 90). Samples will be maintained in a cooler containing dry ice and then placed in a  $\leq -65^{\circ}\text{C}$  freezer until shipped for analysis. At the request of the Sponsor or its designee, serum HGF samples will be batched with VM202 samples, and shipped in

---

a special container with temperature tracking recorder to Charles River Laboratories for analysis.

Charles River Laboratories  
Preclinical Services Nevada  
[name]  
[name]  
[contact]

**4.2.5. COPIES OF VM202 IN WHOLE BLOOD**

---

[REDACTED]

[REDACTED]

[REDACTED]

**4.2.6. FORCED VITAL CAPACITY**

---

Forced Vital Capacity (FVC) is a pulmonary function test that quantifies the volume of air that can forcibly be blown out after full inspiration. It correlates with survival in ALS. FVC will be determined during Screening, on Day 0 before the treatment (injection), on Day 30, Day 60, Day 90, at 6 months and 9 months. FVC measurement will be performed by trained personnel as recommended for ALS clinical trials using standard techniques in the sitting position and expressed as a percentage of the expected value.

**4.2.7. REVISED AMYOTROPHIC LATERAL SCLEROSIS FUNCTIONAL RATING SCALE (ALSFRS-R)**

---

The revised Amyotrophic Lateral Sclerosis Functional Rating Scale (ALSFRS-R) is a validated rating scale for measuring the global function of patients with ALS. It

---

provides a health professional-generated estimate of the patient's degree of functional impairment, which can be evaluated serially to objectively assess any response to treatment or progression of disease. The ALSFRS-R includes twelve questions that ask the physician to rate his/her impression of the patient's level of functional impairment in performing one of twelve common tasks, *e.g.* climbing stairs. Each task is rated on a five-point scale from 0 = can't do, to 4 = normal ability. Individual item scores are summed to produce a reported score of between 0=worst and 48=best. The ALSFRS-R will be conducted at Screening, on Day 0 before the treatment (injection), on Day 30, Day 60, Day 90, at 6 months and 9 months. Details can be found in [Appendix 5](#).

#### **4.2.8. MEDICAL RESEARCH COUNCIL (MRC) SCALE FOR MUSCLE STRENGTH TESTING**

---

The Medical Research Council (MRC) Scale is a validated instrument used in assessing muscle strength. It uses the numeral grades 0 – 5 to characterize muscle strength as follows:

- 0 - No contraction
- 1 - Flicker or trace contraction
- 2 - Active movement, with gravity eliminated
- 3 - Active movement against gravity
- 4 - Active movement against gravity and resistance
- 5 - Normal power

The MRC scale will be used to assess muscle strength in the muscle groups injected with VM202. This assessment will be conducted on Day 0 before the treatment (injection), on Day 30, Day 60, Day 90, at 6 months and 9 months. The muscle groups to be evaluated and the methods of evaluation can be found in [Appendix 6](#).

#### **4.2.9. MUSCLE CIRCUMFERENCE**

---

The muscle circumference of the following groups of muscles will be assessed on Day 0 before the treatment (injection), and on Day 60, Day 90, at 6 months and 9 months. Measurements will be taken bilaterally:

- **Mid-arm:** at the midpoint of a vertical line that joins the acromion process to the olecranon process
- **Mid forearm:** at the proximal one third point of a vertical line that joins the medial epicondyle to the styloid process of the ulna
- **Mid-thigh:** midpoint of a vertical line that joins the anterior superior iliac spine to the superior edge of the patella
- **Mid-leg:** at the proximal one third point of a vertical line that joins the fibular head to the lateral malleolus

The procedures for measuring muscle circumference can be found in [Appendix 7](#).

#### **4.2.10. DYNAMOMETRY**

---

Finger pinch force, grip strength, and lower leg extension will be measured using non-AC powered dynamometers manufactured by Hoggan Health Industries, Inc. Data will be collected on the Data Collection Software Package that works with all the Hoggan FET dynamometers. These measurements will be performed on Day 0 before the treatment (injection), Day 60, Day 90, 6 months, and 9 months.

#### **4.2.11. INJECTION SITE REACTION ASSESSMENT**

Local injection sites reactions will be assessed on Day 0 post injection, Day 7 pre and post injection, Day 14 pre and post injection, Day 21 pre and post injection, Day 30, and Day 60. Any adverse reaction should be reported as an AE.

---

## **5. EVALUATION OF ADVERSE EVENTS**

---

### **5.1. DEFINITIONS**

---

An Adverse Event (AE) is the development of an untoward medical occurrence or the deterioration of a pre-existing medical condition following or during exposure to an investigational product, whether or not considered causally related to the product.

An untoward medical condition can be symptoms (*e.g.*, nausea, chest pain), signs (*e.g.*, tachycardia, enlarged liver) or clinically significant abnormal results of an investigation (*e.g.*, laboratory findings, electrocardiogram).

Conditions or diseases that are chronic but stable should not be recorded on AE pages of the CRF. In addition, changes in a chronic condition or disease that are consistent with natural disease progression are NOT considered AEs and also should not be recorded on AE pages of the CRF. These medical conditions should be adequately documented on the appropriate page of the CRF (medical history and/or physical examination).

An **adverse reaction** means any adverse event caused by a drug. Adverse reactions are a subset of all suspected adverse reactions for which there is reason to conclude that the drug caused the event.

**Suspected adverse reaction** means any adverse event for which there is a reasonable possibility that the drug caused the adverse event. For the purposes of IND safety reporting, ‘reasonable possibility’ means there is evidence to suggest a causal relationship between the drug and the adverse event. A suspected adverse reaction implies a lesser degree of certainty about causality than adverse reaction, which means any adverse event caused by a drug.

A **serious adverse event (SAE)** is any untoward medical occurrence which:

- Results in death;
- Is life-threatening;

- 
- Requires inpatient hospitalization (admission to hospital with a stay > 24 hours) or prolongation of hospitalization (note, elective procedures requiring hospitalization are not considered a SAE);
  - Results in permanent impairment of a body function or permanent damage to a body structure; or
  - Requires medical or surgical intervention to preclude permanent impairment of a body function or permanent damage to a body structure.

Additionally, important medical events that may not result in death, be life-threatening or require hospitalization may be considered SAEs when they jeopardize the subject or require medical or surgical intervention to prevent one of the serious outcomes listed above. Examples of such medical events include: allergic bronchospasm requiring intensive treatment in an emergency room or at home, blood dyscrasias or convulsions that do not result in inpatient hospitalization or the development of drug dependency or drug abuse. Medical and scientific judgment must be exercised when classifying events as serious.

**Life-threatening** means that the subject is, in the view of the Investigator, at immediate risk of death from the AE as it occurred. It does not include an AE which, had it occurred in a more serious form, might have caused death.

**Persistent or significant disability/incapacity** means that the event resulted in permanent or significant and substantial disruption of the subjects' ability to carry out normal life functions.

An **unexpected AE** is an AE, the nature or severity of which is not consistent with the applicable product information (*e.g.*, Investigator Brochure for an unapproved product). Expected means that the event has been previously observed with the test article and is identified and/or described in the applicable product information. It does not mean that the event is expected with the underlying disease(s) or concomitant medications. It is expected that certain disease states will have reoccurring adverse events some of which may be considered expected over time.

---

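### The SAE list in Section 5.1 omits the disability criterion that the same section defines, so a substantial but reversible disability is not serious under any mandatory criterion in its own right

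*Combined protocol and SAP*

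**What the plan says.** Section 5.1 lists five outcomes that make an adverse event serious:

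1. "Results in death"
2. "Is life-threatening"
3. "Requires inpatient hospitalization (admission to hospital with a stay > 24 hours) or prolongation of hospitalization"
4. "Results in permanent impairment of a body function or permanent damage to a body structure"
5. "Requires medical or surgical intervention to preclude permanent impairment of a body function or permanent damage to a body structure"

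A further paragraph allows important medical events to be classed as SAEs. It is worded as something that may be done. It applies when the event jeopardizes the subject, or when intervention is needed to prevent one of the outcomes already listed. The paragraph ends by calling for medical and scientific judgment.

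The section then defines three terms: life-threatening, "Persistent or significant disability/incapacity", and unexpected AE. The second "means that the event resulted in permanent or significant and substantial disruption" of the subject's normal functioning.

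**The concern.** A definition that sits beside the one for life-threatening, which is a listed criterion, appears meant to support a seriousness criterion too. No such criterion is in the list. The omission has content, because the definition reaches disruption that is significant and substantial without being permanent, and the listed impairment items do not.

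This matters because safety and tolerability are the primary endpoint (Section 6.2), and three things turn on the seriousness flag:

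- the investigator's report to the sponsor and CRO within 72 hours, with complete information within 5 calendar days (Section 5.4.1);
- the sponsor's 15-day IND safety report for serious, unexpected suspected reactions (Section 5.4.2);
- the SAE summary (Section 6.2.1).

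Injections go into the hands, arms, thighs and lower legs, 256 per subject in total (Tables 1 and 2). How a temporary loss of limb function should be classified is therefore a fair question to settle in advance. The documents do not report that such losses have occurred.

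**Working it through.** No formula applies; the check is a comparison of texts.

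**Step 1: scope of the list against scope of the definition.** None of the five items mentions disability or incapacity. Items 4 and 5 are the closest, and both are tied to permanence. The definition joins its two limbs with *or*: permanent disruption, or disruption that is significant and substantial. The second limb has no counterpart in the list.

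**Step 2: where the defined term is used.** Life-threatening is list item 2. Unexpected governs IND reporting in Section 5.4.2. The disability term appears nowhere else in the text available for this review, which excludes the sample consent form and the SAE form.

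**Step 3: a test case.** Take a hypothetical subject who loses the use of a hand after injection and later recovers. The subject is not at risk of death, is not hospitalized, and needs no intervention to prevent permanent harm.

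| Route to seriousness in Section 5.1 | Met? |
|---|---|
| Death | No |
| Life-threatening | No |
| Hospital stay > 24 hours, or prolongation | No |
| Permanent impairment or damage | No |
| Intervention to preclude permanent harm | No |
| Important medical event, intervention limb | No: no intervention is needed, and disability is not among the outcomes this limb refers to |
| Important medical event, jeopardy limb | Possible, at the investigator's discretion |
| Disability definition | Described by it if the disruption is significant and substantial, but the definition is not attached to any criterion |

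The event meets 0 of the 5 mandatory criteria. One route remains open, and it is discretionary.

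**Step 4: what happens if that route is not used.** The event is still entered as an AE, because Section 5.2 requires all AEs to be recorded with severity, outcome and relationship. Section 5.2.2 describes the top intensity grade in terms of marked limitation of routine activity, so severe but not serious is a natural coding. The exception is an event judged consistent with natural disease progression: Section 5.1 says this is not an AE at all.

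**Step 5: scale.** One subject is 1/18 = 5.6% of the planned sample and 1/6 = 16.7% of the six subjects at the staged DSMB review. This is the weight of any single subject, and it moves SAE incidence only if that subject has no other SAE. It is not an estimate of how often the problem would arise.

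**The case against.** The strongest reply is that this is a drafting slip with little effect. Investigators will probably read the definition as a seriousness term because of where it stands. The jeopardy limb of the important-medical-event clause does not depend on the list, and the protocol requires judgment in classifying events. Every AE is recorded and graded, injection sites are assessed through Day 60, and nothing restricts the DSMB to SAE counts. No hypothesis is tested.

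Much of this stands, and it limits the finding. A reader might go further than the documents allow in four ways:

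- **That a reversible disability would never count as serious.** It would if it led to a hospital stay of more than 24 hours, prolonged a hospitalization, or needed intervention to preclude permanent harm. It could also be classed as an important medical event.
- **That the suspension rule would miss it because of this gap.** That rule (Section 3.2) names three events: acute anaphylaxis, fever above a stated threshold, and tissue necrosis at the injection site. Disability is not one of them, and adding a seriousness criterion would not change that.
- **That the primary safety result is understated.** The endpoint is safety and tolerability as a whole, not SAE incidence. What is at risk is the seriousness flag and what follows from it.
- **That 5.6 or 16.7 percentage points is the expected distortion.** Those figures are only one subject's share.

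What the reply does not remove is the conflict itself. A probable reading by a careful investigator is not a rule, and "may be considered" language cannot stand in for a listed criterion when reporting deadlines depend on the answer.

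**Conclusion.** The inconsistency is real and should be corrected, preferably before enrollment so that events need not be reclassified later. Section 5.1 defines a seriousness concept and then gives it no effect. A substantial, reversible disability with no qualifying hospital stay and no intervention to preclude permanent harm is serious only if the investigator chooses to class it so. It could then be missing from the SAE summary and from the 72-hour and 15-day reports, while still appearing among the AEs with its severity unless attributed to disease progression.

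The size cannot be given, because the documents supply no rate for such events. The conclusion assumes that the list in Section 5.1 is the operative definition at the site and that the SAE form does not already carry the missing item. The form was not available, so the second assumption is untested.

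**What to change.** Add one item to the SAE list in Section 5.1, stating that an event is serious if it results in "Persistent or significant disability/incapacity", with a pointer to the definition that follows in the same section. Check that the SAE form carries the same criterion, and align it if it does not.

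The change is one line and uses the protocol's own term. It alters no dose, visit or procedure, and it leaves the suspension rule and the natural-progression exclusion as they are. It also brings disability within the outcomes to which the intervention limb of the important-medical-event clause refers.

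The downside is that the SAE count, and with it expedited reporting, may rise slightly.

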## 5.2. ASSESSMENT OF AEs

---

All AEs experienced by study subjects, regardless of severity, which occur between the first study drug administration and the 9 month follow-up visit of the study must be recorded on the AE form provided with the CRF. This will include the following information:

- Description of the AE
- Date of onset
- Duration
- Frequency
- Severity
- Seriousness (yes/no)

- 
- Treatment
  - Outcome
  - Relationship to study medication, injection procedure and/or underlying disease

All AEs and SAEs must be followed until resolution, or the condition stabilizes. The Investigator is responsible to ensure that follow-up includes any supplemental investigations as may be indicated to elucidate as completely as possible the nature and/or causality of the AE or SAE. This may include additional laboratory tests or investigations, histopathological examinations, or consultation with other health care professionals. The Sponsor or its designee may request that the Investigator perform or arrange for the conduct of supplemental measurements and/or evaluations.

#### **5.2.1. AE CAUSALITY**

---

The study Investigator will determine whether an AE is related or unrelated to study medication, the procedure (intramuscular injection) and / or the underlying disease using the following criteria:

**Not related:** An adverse event that is not related to the use of the test article or administration procedure.

**Possibly related:** An adverse event that might be due to the use of the test article or administration procedure. An alternative explanation, *e.g.*, concomitant study product(s), concomitant disease(s), is inconclusive. The relationship in time is reasonable; therefore, a causal relationship cannot be excluded.

**Probably related:** An adverse event that might be due to the use of the test article or administration procedure. The relationship in time is suggestive. An alternative explanation is less likely, *e.g.*, concomitant drug(s), concomitant disease(s).

**Definitely related:** An AE that is due to the use of the test article or administration procedure. The event cannot be reasonably explained by an alternative explanation – *e.g.*, concomitant drug(s), concomitant disease(s).

#### **5.2.2. AE INTENSITY**

---

The intensity of the AE/SAE will be defined by the following criteria:

Mild: The AE is noticeable to the subject but does not interfere with routine activity.  
Moderate: The AE is discomforting and interferes with routine activity.  
Severe: The AE significantly limits the subject's ability to perform routine activities despite symptomatic therapy.

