**SAFETY**

Adverse events (including serious adverse events, and adverse events leading to treatment discontinuation) throughout the 9 months follow-up will be described according to severity and to their relationship with the study drug and injection procedure. Descriptive statistics will be used to characterize safety parameters.

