### **3.4.4. PROHIBITED CONCOMITANT MEDICATIONS**

#### **3.4.4.1. MEDICATION THAT MAY INTERFERE WITH VM202 BIOACTIVITY**

COX-1 and COX-2 inhibiting drugs may interfere with the bioactivity of VM202, and are therefore prohibited from use during the study. Other than the maximal 81 mg daily dose of aspirin (acetylsalicylic acid), subjects must agree to not take any of these drugs until completion of the 9 month follow-up visit. The patient needs to be advised that common over the counter medications that are prohibited include: Bayer (> 81mg), Excedrin, Aleve, Advil (motrin, ibuprofen). A more complete list of the excluded medications, including the washout period, can be found in [Appendix 3](#).

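### Section 5.2.2 ties the Severe grade to failed symptomatic therapy, so a limiting adverse event that was untreated, or relieved by treatment, can be graded Moderate

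*Combined protocol and SAP*

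**What the plan says.** Section 5.2.2 introduces the scale for all events, serious ones included: "The intensity of the AE/SAE will be defined by the following criteria". It has three grades. The lowest, Mild, is for an event that the subject notices but that leaves daily routine undisturbed. The middle grade is worded "Moderate: The AE is discomforting and interferes with routine activity". It sets no upper limit and does not mention treatment. The top grade, Severe, asks for marked limitation of the "ability to perform routine activities despite symptomatic therapy".

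No other intensity scale appears in the protocol. Nothing says that an event is graded at its worst, and nothing covers an event that was untreated or that resolved on treatment.

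Section 5.2 lists the items on the adverse event form. Severity, seriousness and treatment are separate entries. Under Safety, the synopsis says that adverse events "will be described according to severity and to their relationship with the study drug and injection procedure". Section 6.2.1 says that categorical variables are summarised as numbers and percentages of patients. Safety and tolerability are the primary endpoint (section 6.2).

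**The concern.** An intensity grade should say how bad the event was. Here the top grade also asks whether therapy was given and whether it worked; the two lower grades do not. Two subjects with the same limitation can therefore receive different grades because one took a symptomatic remedy and the other did not, or because the remedy worked in one and failed in the other.

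This matters because the trial is single-arm and plans no hypothesis testing (section 6). The descriptive safety summary is the result, and severity is one of the two axes on which the synopsis says events will be described. Section 4.2.11 sends adverse injection-site reactions to the adverse event record without a local-reaction scale of their own, so they too are graded under 5.2.2.

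**Working it through.** No figure in the plan depends on this definition, so there is nothing to reproduce. The main check is to apply the three definitions, as worded, to the possible cases.

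**Step 1: grade the cases.** Take an event that is discomforting and, at its worst, significantly limits routine activity.

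| Case | Meets Mild? | Meets Severe as worded? | Grade as worded | Grade by limitation alone |
|---|---|---|---|---|
| Treated, limitation persists | No, it interferes | Yes | Severe | Severe |
| Never treated | No, it interferes | No, there was no therapy for the limitation to persist through | Moderate | Severe |
| Treated and relieved | No, it interferes | No, the limitation did not persist through therapy | Moderate | Severe |

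In the last two rows Moderate is the only grade left, and the event meets it, because Moderate asks only for discomfort and interference and has no upper limit.

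**Step 2: direction.** The therapy clause is an extra condition on Severe. An extra condition can take events out of a category but cannot put any in. On this account the Severe count can be too low and cannot be too high.

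**Step 3: scale.** Inputs: 18 evaluable subjects (section 3.3), and summaries by number and percentage of patients (section 6.2.1).

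- One subject moved from Severe to Moderate changes the Severe proportion by 1/18 = 5.6 percentage points.
- With exact (Clopper-Pearson) 95% limits, 1 of 18 is 5.6% (0.1% to 27.3%) and 0 of 18 is 0% (0% to 18.5%). Losing the only Severe subject therefore lowers the upper limit from 27.3% to 18.5%.
- This counts each subject once, at the highest grade. A subject who also has an event properly graded Severe does not move.

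**Step 4: can the size be estimated?** No. It depends on two quantities that the documents do not give: the proportion p of subjects with a significantly limiting event, and the share s of those whose event is untreated or relieved. If subjects are independent and the wording is applied literally, the chance that at least one of 18 is shifted is 1 − (1 − p·s)^18.

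- Assume p = 10% and s = 25%: p·s = 0.025, and 1 − 0.975^18 = 37%.
- Assume p = 30% and s = 75%: p·s = 0.225, and 1 − 0.775^18 = 99%.

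These are assumed values. The width of the range shows that the result reflects the assumptions and is not an estimate for this trial.

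**Step 5: what else uses the grade.** Section 5.1 defines seriousness by outcome (for example death, hospitalisation or permanent impairment), and section 5.2 records it as its own item. The suspension rule in section 3.2 lists specific serious events and does not refer to intensity. Severity does enter the definition of an unexpected event in section 5.1, but the expedited reports in section 5.4.2 also require a serious event, or a fatal or life-threatening one.

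**The case against.** The strongest reply is that the therapy phrase describes degree, meaning limitation that is present even with whatever relief is used, and that an investigator would grade a plainly incapacitating event as Severe whether or not it was treated. That is possible, and the CRF guidance is not among the documents. But the protocol says that these criteria define intensity, and it gives no instruction for untreated or relieved events. If some graders apply the clause strictly and others do not, the grades become inconsistent.

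A second reply is that affected events can be traced, because the form records treatment, duration and outcome beside severity. This is partly right: in 18 subjects, Moderate events can be listed with the treatment given. However, the listed items do not include intensity before treatment, so the grade at worst may not be recoverable.

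Three stronger readings are tempting, and the documents do not support them:

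- A reader might infer that untreated local reactions are likely, because section 3.4.4.1 says "COX-1 and COX-2 inhibiting drugs may interfere with the bioactivity of VM202, and are therefore prohibited from use during the study". That section and Appendix 3 restrict particular drug classes, not all symptomatic therapy. Acetaminophen on its own is not listed; it appears only as part of a combination with aspirin. Moreover, if permitted therapy works less well, more treated events stay limiting and so qualify as Severe. The restriction makes untreated events plausible and no more.
- A reader might infer that a planned primary severity table is biased. Section 6.2.1 names no by-severity table. The commitment is the synopsis statement, and any understatement needs at least one such event and literal grading.
- A reader might infer that serious events would be hidden or the suspension rule weakened. Neither depends on the intensity grade.

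**Conclusion.** The point stands as a defect of wording that can lower the Severe count and cannot raise it. It rests on a literal reading of 5.2.2 and on the absence of any worst-intensity rule. The description of adverse events by severity can read too low; whether it will, and by how much, cannot be established from the documents. For scale, each subject shifted is worth 5.6 percentage points of the planned 18. There is no control arm, and no planned analysis compares symptomatically treated with untreated subjects, so no comparison is biased. The change is worth making because safety is the primary endpoint and the correction is simple. It is not a reason to hold the trial.

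**What to change.** In section 5.2.2, delete the closing condition about symptomatic therapy from the Severe definition, so that Severe rests on the degree of limitation alone. Add one sentence: each adverse event is graded at its worst intensity, whether or not it was treated. Keep treatment in its existing item on the adverse event form.

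The cost is one phrase and one sentence in 5.2.2, and a matching edit to the CRF guidance. No data item is added, and no dose, schedule or treatment rule changes. The downside for the sponsor is that the Severe count may look slightly less favourable. The edit is best made before grading starts; if grading has begun, earlier Moderate events need to be reviewed against the new wording.
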